***If "Yes" what websites will you access to obtain the data?***

***Please know that it is your responsibility to check the terms of service of any websites from which you plan to collect data to determine whether your planned data collection is compatible with the terms of service.***

Similar to other online social networks, TheMighty owns the user data and is therefore permitted to conduct research on the data. We will only conduct research using secondary data of individuals who have consented to being part of the study. The relevant language from the terms of service is copied below:

"USE OF CONTENT SUBMITTED BY YOU

BY UPLOADING, POSTING, SENDING OR SUBMITTING PHOTOGRAPHS, PICTURES, IMAGES OR ANY OTHER CONTENT INCLUDING, WITHOUT LIMITATION, GRAPHICS, VIDEO, DATA, TEXT, FILES, LINKS, SOFTWARE, MUSIC, SOUND ("CONTENT"), YOU ARE CONSENTING TO BE BOUND BY THESE TERMS OF USE. IF YOU DO NOT AGREE, DO NOT UPLOAD, POST, SEND OR SUBMIT ANY CONTENT TO THIS SITE.

You agree that any Content you upload, post, email, transmit or otherwise make available via the Service is non-confidential and that we shall have a perpetual, worldwide, non-exclusive license to use any such Content in connection with the Service and our business (and any successor), including without limitation for promoting and redistributing part or all of the Service (and derivative works thereof) in any media formats and through any media channels. You also hereby grant each User a non-exclusive license to access your Content through the Site, and to use, reproduce, distribute, prepare derivative works of, display and perform such Content as permitted through the functionality of the Site and under these Terms of Service. The submission of any materials to us irrevocably waives any and all "moral rights" in such materials, including the rights of paternity and integrity."

The full terms of service are here for your reference:

<https://intercom.help/themighty/en/articles/1781523-terms-and-conditions>

5.27 Is the data publicly available on the internet (i.e., freely available without permission, sign-in, or other restrictions)?

Yes

No

5.28 Do you plan to access any data that is Protected Health Information (PHI) under the HIPAA law (for example, data held by a hospital or other healthcare provider or insurer)?

Yes

No (*skip to question #5.31*)

5.29 Which organization will provide the HIPAA PHI to you?

5.30 How will permission to allow the use/disclosure of individual's protected health information (PHI) be obtained?

**HRP-330 WORKSHEET: HIPAA, which may be found in the ESTR library, provides an overview of items pertaining to HIPAA that may be helpful to the study team.**

5.31 Do you plan to access any data that is FERPA protected (data that are held as education records by an educational institution)?

Yes

No

**HRP-331 WORKSHEET: FERPA COMPLIANCE which may be found in the ESTR library provides an overview of items pertaining to FERPA that may be helpful to the study team.**

5.32 Do you plan to obtain data that has been obtained under "Broad Consent" (as part of the 2018 Requirements)?

Yes

No

Uncertain

#### USING PREVIOUSLY COLLECTED BIOLOGICAL MATERIALS

*Please complete this section if you are receiving biological material that has already been collected. This section does not pertain to biological material that is being collected through interaction or intervention as part of this study. Skip this section if not applicable.*

5.33 Indicate the identifiability of the biological materials:

Will not contain any direct or indirect identifiers; will be anonymous.

Will not be identifiable, but there will be a code held by the data source that links to the identities; will be coded.

- Will contain direct or indirect identifiers, but this research team will remove them upon receipt; will be de-identified data.
- Will contain direct identifiers; will be identifiable.

5.34 How will you obtain the material? (check all that apply)

- Residual clinical material
- Material obtained from a vendor
- Material that was collected as part of another research study (***please see below***)
- Other – (***see below***)

***If you chose “another research study” provide the title/name of the previous research study and which institution and researcher collected the specimens for the previous study. If the specimens were collected in a previous Harvard University research study, provide the ESTR number assigned to that study.***

***If “another research study” or “Other” please specify:***

5.35 Will the material consist of any of the following? (check all that apply)

- Embryonic tissue
- Embryonic stem cells
- Stem cells
- Fresh human fetal tissue
- None of the above

5.36 Provide an overview of the types of variables that will accompany the biological materials (for example, identifiable data such as names, date of birth, addresses, or any data that are considered sensitive).

## DEVICES

*Skip this section if not applicable.*

5.37 List the device(s) that you plan to use in this study (add additional lines as necessary):

Device Brand Name	Generic/Common Name	Manufacturer	Purpose	Function/Operation

5.38 Is the device(s) that you plan to use FDA-approved/cleared?

- Yes
- No

5.39 If any of the devices that you plan to use require a certified professional to operate, please explain who is certified to operate this device and whether they are on your study team.

***Please complete HRP-307 WORKSHEET: DEVICES which may be found in the ESTR library and attach to the “Local Site Documents” section in the ESTR SmartForm.***

## DRUGS

*Skip this section if not applicable.*

5.40 List the drug(s) or biologic(s) that you plan to use in this study (add additional lines as necessary):

Drug/Biologic Brand Name	Generic/Common Name	Manufacturer	Purpose	Function/Operation

5.41 Is the drug(s)/biologic(s) that you plan to use FDA-approved/cleared?

Yes  
 No

5.42 Please explain who is qualified to dispense this drug/biologic and whether they are on your study team.

***Please complete HRP-306 WORKSHEET: DRUGS which may be found in the ESTR library and attach to the “Local Site Documents” section in the ESTR SmartForm.***

## 6. RISK AND BENEFIT ASSESSMENT

6.1 Describe the foreseeable risks associated with your study. Please include discussion of any physical risks and non-physical risks, such as economic, psychological, social, and legal harms.

1. Asking subjects about suicide may cause distress in some patients.
2. Despite the fact that the articles selected by TheMighty decrease the level of suicidal ideation collectively, there may be certain subjects who experience increased SI after reading the assigned articles.
3. If there is mismanagement of data, user names and/or emails may be associated with their activity in the research database, and may become visible to the researchers

6.2 Describe the steps that you will take to minimize risks to your participants (for example, using pseudonyms or a coding system, etc.)

1. In order to address this concern, we will take several measures. First, during the consenting process, we will include language that warns subjects that some of the survey questions may induce distress. Second, we will make sure that subjects can easily exit the study at any time.

It is important to note that research has demonstrated that asking patients about suicide does not appear to increase the level of suicidality (Dazzi et al, 2014). The research team will meet regularly to review data and any adverse effects. [name], licensed clinical psychologist, will oversee these meetings.

2. At the end of each survey, we will provide users with a pop-up that provides information on how to get in touch with a suicide hotline.
3. We will institute an automatic data cleaning process that ensures that all names and emails will be deleted from the database before any researchers have access.

6.3 Are provisions needed for medical and/or psychological support resources (for example, in the event of research-related distress or incidental findings)?

Yes

No

6.4 If applicable, what steps will you take if a participant becomes distressed during your study or reports intent to harm themselves or others?

Should a participant report elevated suicidal ideation, a pop-up screen will be triggered and will provide contact information for a suicide hotline

6.5 Describe any potential direct benefits to participants in the study. If there are no individual benefits, indicate as such.

The intent of this study is to evaluate the efficacy of a reading certain articles in reducing STBs. Should it be successful, patients may experience fewer STBs. Participants may benefit from developing insight as to how reading materials affect their thoughts and feelings.

6.6 Describe any potential benefits to society.

If successful, this study will validate the first social media intervention that decreases suicidal thoughts and behaviors. We believe that validating this type of intervention would be particularly impactful given the ease with which clinicians can recommend this free intervention.

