## 9. SCREENING

9.1 Will you be screening participants for eligibility? *Note that If you are using inclusion or exclusion criteria, you will be “screening” individuals in order to determine who is eligible.*

Yes

No (*skip to next section*)

9.2 Explain what your screening criteria will be and how you will conduct the screening process.

When new users access certain types of articles, a dialog box will appear asking them if they are interested in participating in a study aimed at helping The Mighty understand the impact of the articles posted by other users on its platform and asking if they would like more information. Prospective participants who respond “yes” will be prompted to fill out a brief screening survey to indicate their age and history of suicidal thoughts and behaviors.

9.3 Do you plan to destroy the data from people who participate in the screening process and do not qualify to be in the study as soon as the screening process is over?

Yes

No (*see below*)

***If “No” explain why you will keep the data collected in the screening process for people who are not eligible to participate in this study.***

We plan to destroy data from participants who participate in the screening process and do not qualify for the study after the enrollment has ended. However, we would like to retain screening data from the participants who do not qualify for the study to ensure that they do not attempt to re-enroll and provide false screening information at a later time.

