10.3 Where will the consent or an agreement to participate process take place?

In-person  
 Online  
 Over the telephone  
 Other (**see below**)

*If other, please describe:*

10.4 Who will obtain consent or an agreement to participate from participants? *Will the Principal Investigator, other members of the Harvard University research team, collaborating researchers from other institutions, or another third party (such as a survey firm) obtain consent?*

The consent form will be an automatic pop-up on TheMighty's website, which will be managed by team members at TheMighty.

10.5 Describe the process that will be used to obtain consent or an agreement to participate.

Consent will be obtained digitally, by simply having the participant click "agree" before they can continue. There will be an option for users to print or download the consent form for their records.

10.6 Describe how you will assess comprehension of the research and what it means to participate, including understanding of the voluntary nature of participating.

Research subjects can decline participation. We will include language that explicitly states that participation is entirely voluntary, and that refusal to participate will not limit their access to the resources on the website in any way

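### The protocol states no hotline display point for a participant who leaves a survey or the study early in distress; adding one is a minor, low-cost safety improvement

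*Protocol*

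**What the plan says.** Protocol 6.1 lists two relevant foreseeable risks. The first is that "Asking subjects about suicide may cause distress in some patients". The second is that "there may be certain subjects who experience increased SI after reading the assigned articles".

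Protocol 6.2 answers them in matching numbered items. Against distress from the questions, item 1 offers a warning at consent and says that "we will make sure that subjects can easily exit the study at any time". It adds regular team review of data and adverse effects, overseen by a licensed clinical psychologist. Against increased ideation after reading, item 2 says: "At the end of each survey, we will provide users with a pop-up", and the pop-up explains how to reach a suicide hotline.

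The question at 6.4 asks "what steps will you take if a participant becomes distressed during your study" or reports intent to harm. The answer is: "Should a participant report elevated suicidal ideation, a pop-up screen will be triggered", again with hotline contact details. The threshold for elevated ideation and the moment at which the screen fires are not given.

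The SAP does not deal with safety resources.

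**The concern.** Both stated display points depend on the participant continuing. One needs the survey to be finished; the other needs an answer that reports elevated ideation. Leaving is the response that 6.2 itself offers to someone upset by the questions, and a person who takes it may reach neither point in that session. The 6.4 answer deals with reported ideation and does not take up the distress half of its question.

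Under 7.2, everyone enrolled has thought about suicide in the past 12 months, and only those reporting intent of 7 or more on a 10-point scale are excluded. The trial runs online, and 6.2 has names and emails deleted before researchers have access. The team's review meetings are therefore not described as help in the moment; the pop-ups are the only such help that the protocol describes. The stake is a missed opportunity to offer a hotline when someone leaves upset. The trial's estimates and error rates are not affected.

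**Working it through.** The plan has no figure to reproduce here, so the check sets the stated display points against the ways a participant can leave.

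**Stated display points**
- A: end of each survey (6.2 item 2).
- B: report of elevated suicidal ideation (6.4).

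**Routes out**
1. *Finishes the survey.* A applies, and B as well if ideation is elevated.
2. *Reports elevated ideation, then leaves before the end.* B applies if the screen fires on the answer. If it fires only on submission, it does not. The timing is not stated.
3. *Leaves before the ideation item, or after it without reporting elevated ideation.* Neither A nor B applies at that moment. Section 5.1 lists ideation among the survey constructs but does not give item order.
4. *Reads the article and does not take the post-article survey.* Neither applies at that moment. An Active Treatment (AT) participant who completed the pre-article survey has just passed point A.
5. *Withdraws from the study.* No display is stated.

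**Exposure before leaving**
- Under 9.2, prospective participants "will be prompted to fill out a brief screening survey to indicate their age and history of suicidal thoughts and behaviors". If item 2 of 6.2 covers this survey, every enrolled participant has seen the hotline at least once.
- Under 5.3, all qualifying and consenting participants complete a baseline battery (T0). If item 2 covers T0, anyone who finishes it has seen the hotline.
- If neither counts, the first completed daily survey supplies it.

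The number of enrolled participants who never saw the hotline before leaving may therefore be zero. What remains is the lack of a stated display at the time of leaving.

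**Scheduled occasions**
Section 5.1 gives AT participants at least 1 article per day for 5 to 14 days, with a survey before and after each. At exactly 1 article per day:
- Article surveys: 5 × 2 = 10, up to 14 × 2 = 28.
- Of these, post-article surveys: 5 × 1 = 5, up to 14 × 1 = 14.

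These are minimum counts for the stated durations at that rate; 5.1 allows article number and frequency to change after the feasibility trial. They count surveys that could be left unfinished. They do not count exits, distress events or people without information.

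**The case against.** The strongest reply is that this is silence, and silence does not show that the hotline is absent at exit. Section 8.2 refers to two files, the consent form and the recruitment language and surveys, and neither is in this copy. Either could carry hotline details. Section 10.5 adds: "There will be an option for users to print or download the consent form for their records", so a participant may hold a copy. The 6.3 tick-box answer cannot be read here. This stands, and it limits the point to what the protocol states.

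Second, the exit offered in 6.2 reads most naturally as withdrawal from the study, not as leaving one survey, and each named risk already has its own measure. The distinction is fair. Neither kind of exit has a stated display point, however, so the gap does not depend on which is meant.

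Third, other safeguards exist: the distress warning at consent, the review overseen by a psychologist, the intent exclusion, and repetition of the hotline at every completed survey. These reduce the importance of the gap and support a low rating. None of them is a display at exit.

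Fourth, no exit screen is described anywhere, and someone who closes the page would not see one. This also stands. It is why the emails have to carry most of the fix, and why the fix cannot fully close the gap at the moment of leaving.

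A reader might infer that distressed participants are left without hotline information, or that the 10 to 28 scheduled surveys measure how often this happens. The documents support neither reading. They do not rule out display at exit, most participants will have seen the hotline before, and no rate of exit or distress is given.

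**Conclusion.** The point holds as a minor one, for consideration. The protocol states two hotline display points and none for a participant who leaves a survey or the study early because of distress, although it offers exit against distress and is asked directly about distress at 6.4.

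No headcount can be given. The conclusion assumes that the files not in this copy do not already provide the information at exit. If they do, one sentence in the protocol would record it. The residual gap is smallest if the screening survey or T0 ends with the pop-up and if the 6.4 screen fires as soon as the answer is given; the protocol settles neither. Nothing here bears on sample size, randomization or the planned analyses.

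**What to change.** Add to both 6.2 and 6.4:

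> The hotline information given in the end-of-survey pop-up will also appear in every study email in both arms, next to each assigned article, and on any survey-exit or study-withdrawal screen the platform uses.

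Putting it in 6.4 as well completes the answer to the distress half of that question. The emails matter most, because they do not depend on an exit screen and 5.1 already uses email to send surveys. The display beside the article reaches someone who stops after reading. During the randomized period it would be seen only in the AT arm, so it should be described as part of what that arm receives; Control participants would see it when they get the articles later.

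The cost is a small template change and slightly longer emails, with no added staff, visits or questions. That is a judgement: the survey tool is built by the platform company (5.4), and the documents give no cost. The remaining limit is that someone who closes the page would see the information in the next email, not at that moment.

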## 7. CHARACTERISTICS OF THE STUDY POPULATION

7.1 Indicate the estimated number of participants, by subgroup if applicable. *If it is not possible to estimate the number of participants (e.g., open online survey), please indicate that it is not possible and provide an explanation of why it is not possible.*

For the initial feasibility trial, we will enroll 50 users in order to test out operations. After process optimization (adjusting timing of sending articles, number of articles sent, etc.), we plan to recruit a

total of 1000 participants for the RCT. Half (500 participants) will be randomized to the AT Condition, and half will be randomized to the Control Condition.

7.2 Describe the criteria for enrollment – Will you be limiting your enrollment to a certain age range, gender, people with certain health conditions, etc.? Please also describe any criteria that will exclude people from enrollment.

Enrollment Criteria: In order to qualify for the study, participants must report:

- having thought about suicide in the past 12 months, and
- that they are at least 18 years old
- English is primary language

Exclusion Criteria: Prospective participants will be excluded from the study if they report:

- a high level of suicide intent (as indicated by a 7 or greater on a 10-point scale of intent to act on suicidal thoughts)

7.3 Are there any potential vulnerable populations or individuals proposed for involvement in the research? (check all that apply)

- Children
- Wards of the State
- Prisoners/Detainees
- Pregnant Women
- Adults not Competent to Consent
- Non-English Speaking
- Employees of Harvard University (as a focus of the study)
- Undergraduate Students of Harvard University (as a focus of the study)
- Staff or students that are part of your lab or for whom you provide oversight
- Other – (see below):

*If “Other” please specify:*

---

#### CHILDREN

*Skip this section if not applicable.*

7.4 What is the age range of children participating in your study?

7.5 Are there any special considerations that need to be taken into account? For example, do the children have a learning disability?

---

**PRISONERS**

*Skip this section if not applicable.*

7.6 Describe any advantages that prisoners may accrue through their participation in the research, especially in comparison to the general living conditions, medical care, quality of food, amenities, and earning opportunities in the prison.

7.7 Explain whether the risks of the research are commensurate with risks that would be accepted by non-prisoner research participants.

---

**EMPLOYEES OR STUDENTS OF HARVARD UNIVERSITY**

*Skip this section if not applicable.*

7.8 Explain how you will minimize the potential for employees and/or students of Harvard University to feel coerced or experience undue influence to participate in the research.

**8. RECRUITMENT**

8.1 Will potential participants be provided with information about the study?

Yes (*see below*)  
 No (*skip to next section*)

*If “Yes” indicate how, when, where, and by whom participants will be recruited. If you are recruiting from a Harvard University Study Pool, describe how you meet their requirements.*

New users who open certain articles will be recruited by a pop up screen. Patients can easily close the screen and ignore the study if they so choose. There will also be an option for users to prevent further pop ups.

8.2 Are there any materials that will be used to recruit participants (e.g., websites, emails, posters, oral scripts)?

Yes (*see below*)

No

***If yes, list the materials by document name here, and be sure to attach copies to the “Consent and Recruitment Materials” portion of the “Local Site Documents” section in the ESTR SmartForm.***

Please refer to the file “Consent Form” and “Recruitment Language and Surveys”

***HRP-315 WORKSHEET: ADVERTISEMENTS which may be found in the ESTR library provides an overview of items pertaining to advertisements that may be helpful to the study team.***

